9.6 Variables

Study endpoints will be reported using descriptive statistics of distribution, central tendency and dispersion as appropriate for the data collected, as outlined in Section 0.

The study endpoints and dataset required to address the study objectives are summarised in Table 4 (please note that the response categories listed below are indicative only; the final list to be collected will be specified in the case report form (CRF)/electronic CRF (eCRF) and associated guidelines).

Table 4. Endpoints and dataset required to address the study objectives

Endpoint to address the primary objective	Dataset required to address the primary objective
Endpoint(s) and dataset required to address the primary objective: To quantify the total time spent by HCPs in the preparation and administration of a single dose of ERT (with agalsidase alfa and agalsidase beta) in patients with FD.	
Primary endpoint: Summary measures of the total time spent by HCPs in the preparation and administration of a single dose of ERT in patients with FD; stratified by country and by ERT product (agalsidase alfa or agalsidase beta). Secondary endpoints: 
 Summary measures of the time spent by HCPs on the following tasks associated with the preparation and administration of a single dose of ERT (with agalsidase alfa or agalsidase beta) in patients with FD: 
 Pre-administration patient consultation. 	For each episode of care: 
 Name/s of observer Patient and staff ID Episode date Episode setting (hospital / infusion centre / primary healthcare centre / primary healthcare centre (preparation and set-up) with home infusion) / other (specify) ERT product administered: agalsidase alfa (Replagal®, Shire or biosimilar) or agalsidase beta (Fabrazyme®, Sanofi Genzyme or biosimilar) ERT dose administered. Pre-medications administered


 ○ Infusion (and pre-medication) preparation activities. ○ Administration of ERT (and pre-medications). ○ Monitoring of patient during and after administration. ○ Completion of clinical documentation. ○ Any other ERT-administration related activities. ● Distribution of the roles of HCP (physician / nurse / nurse assistant or healthcare assistant / pharmacist / pharmacy assistant / other) involved in each task. ● Summary measures of the ERT dose administered. 	
 ● Activities associated with the preparation and administration of ERT: ● Pre-administration patient consultation: 
 ○ Time patient arrived in clinic room. ○ Time patient left clinic room. ○ Start and end time of patient consultation with HCP for pre-treatment assessment. ○ Start and end time of prescription writing (if additional to consultation time with patient). ○ Start and end time of pre-administration clinical documentation (if additional to consultation time with patient). ○ Role of HCP(s) involved (physician / nurse / nurse assistant or healthcare assistant / other [specify]). ● Infusion (and pre-medication) preparation activities: 
 ○ Start and end time of infusion (and pre-medication) preparation activities (note: the following activities [as appropriate] will be included
---	---

	
in the total time, but the time for each separate activity will not be recorded]: pre-dispensing prescription review, label generation, collation of items prior to assembly, assembly of item/drug reconstitution, labelling of containers, accuracy check, prescription delivery).
 
○ Role of HCP(s) involved (physician / nurse / nurse assistant or healthcare assistant / pharmacist / pharmacy assistant / other [specify]).● ERT (and pre-medication) administration:
○ Time patient arrived in clinic for ERT administration○ Time patient left clinic following ERT administration○ Start and end time of pre-medication administration.○ Start and end time of ERT infusion.○ Start and end time of HCP activity for administration of IV agalsidase alfa or agalsidase
--	---

	
beta (including administration of pre-medications).
 
○ Start and end time of HCP activity for patient monitoring during agalsidase alfa or agalsidase beta infusion○ Role of HCP(s) involved (physician / nurse / nurse assistant or healthcare assistant / pharmacist / pharmacy assistant / other [specify]). 
● Post-administration assessment and documentation:
○ Start and end time of HCP activity for post-treatment patient assessment / monitoring.○ Start and end time of HCP activity for completion of clinical documentation.○ Role of HCP(s) involved (physician / nurse / nurse assistant or healthcare assistant / pharmacist / pharmacy assistant / other [specify]).● Other ERT-administration related activities
○ Start and end time of HCP activity for any other ERT-
--	---

	
administration related activities (specify).
 
 ○ Role of HCP(s) involved (physician / nurse / nurse assistant or healthcare assistant / pharmacist / pharmacy assistant / other [specify]).
Endpoints to address the secondary objectives	Dataset required to address the secondary objectives

Secondary objective 1: To quantify the total patient time, costs (i.e. out-of-pocket expenses) and work-related absence associated with attendances for the administration of a single dose of ERT (with agalsidase alfa or agalsidase beta) in patients with FD.
	

 ● Summary measures of the total patient time associated with attendance for the administration of a single dose of ERT (with agalsidase alfa or agalsidase beta) in patients with FD. To include: ● Time spent travelling to and from the hospital or treatment centre ● Time spent collecting ERT from pharmacy (where relevant) ● Time from arrival in hospital/treatment centre to departure ● Time from arrival in hospital/treatment centre to start of ERT infusion ● In addition, if the patient started/delivered their ERT infusion at home following set-up at a primary healthcare centre, the 	
Patient responses to the bespoke study questionnaire:
 
 ● Patient ID ● Date of episode ● Patient employment status (employed full time / employed part time / unemployed / retired / student / home-maker) ● Were they accompanied to the hospital or treatment centre (by a relative or caregiver) or did they attend alone (accompanied / alone) ● Time left home/work to travel to hospital or treatment centre ● Time arrived at hospital or treatment centre ● Time of start of ERT infusion.


following will also be included in the total patient time:
 
 Duration of ERT infusion and any home-based post-administration activities. Time spent travelling to and from treatment centre after ERT infusion (only if patient returned to treatment centre after ERT infusion) Time spent at treatment centre after ERT infusion. Summary measures of the total cost to patients (i.e. out-of-pocket expenses) associated with attendance for the administration of a single dose of ERT (to include the costs of travel / parking / subsistence / other costs). Distribution of patient employment status and whether the patient attended the ERT administration visit accompanied by a relative/caregiver or alone. Proportion of patients with work absence due to attendance for this ERT episode and number of paid / unpaid hours absent. 	
 Time left hospital or treatment centre to travel back to home/work. Time arrived back at home/work. 
Whether patient returned to work on the day of the infusion or the following day. If the patient started their ERT infusion at home following set-up at a primary healthcare centre, the following will also be collected:
 
 Start and end time of ERT infusion Start and end time of any post-administration activities. Time left home/work to return to hospital or treatment centre (if relevant) Time arrived back at hospital or treatment centre (if relevant) Time left hospital or treatment centre to travel back to home/work Time arrived back at home/work Did patient take any time off work to attend this ERT episode? If yes, number of paid / unpaid hours absent from work. Number of hours worked during ERT infusion (if relevant). Costs (i.e. out-of-pocket expenses) incurred by the patient that were directly related to this ERT administration episode (to include
--	--

	costs of travel / parking / subsistence / any other costs).
Secondary objective 2: To quantify the total caregiver time costs (i.e. out-of-pocket expenses) and work-related absence associated with accompanying a patient with FD for the administration of a single dose of ERT (with agalsidase alfa or agalsidase beta).	

 Summary measures of the total caregiver time associated with accompanying a patient with FD for the administration of a single dose of ERT (with agalsidase alfa or agalsidase beta). To include: Time spent travelling to and from the hospital or treatment centre Time spent collecting ERT from pharmacy (where relevant) Time from arrival in hospital/treatment centre to departure Time from arrival in hospital/treatment centre to start of patient's ERT infusion In addition, if the patient started/delivered their ERT infusion at home following set-up at a primary healthcare centre, the following will also be included in the total caregiver time (if the caregiver was involved in the activity): Duration of ERT infusion and any home-based post-administration activities. Time spent travelling to and from treatment centre after ERT infusion (only if patient returned to treatment centre after ERT infusion and was accompanied by a caregiver) 	
Caregiver responses to the bespoke study questionnaire:
 
 • Caregiver ID and patient ID • Date of episode • Caregiver sex (male / female) • Caregiver age category (<20 years / 20<30 years, 30<40 years, 40<50 years, 50<60 years, 60<70 years, 70<80 years, 80 years or over) • Does the caregiver also have FD? • Caregiver employment status (employed full time / employed part time / unemployed / self-employed / retired / student / home-maker) • Caregiver relationship to patient (parent / spouse or partner / son or daughter / other relative / friend or neighbour) • Type and frequency of care or support provided by the caregiver to the patient with FD • Time left home/work to travel to hospital or treatment centre • Time arrived at hospital or treatment centre • Time of start of ERT infusion


 • Time spent at treatment centre after ERT infusion. • Summary measures of the total cost to caregivers (i.e. out-of-pocket expenses) associated with accompanying a patient with FD for the administration of a single dose of ERT (to include the costs of travel / parking / subsistence / other costs). • Distribution of caregiver age, sex, employment status, relationship to the patient with FD, type/frequency of support provided and proportion with FD. • Proportion of caregivers with work absence due to accompanying the patient for this ERT episode and number of paid / unpaid hours absent. 	
 • Time left hospital or treatment centre to travel back to home/work • Time arrived back at home/work. 
If the patient started their ERT infusion at home following set-up at a primary healthcare centre, the following will also be collected (if the caregiver was involved in the activity):
 
 • Start and end time of ERT infusion • Start and end time of any post-administration activities. • Time left home/work to return to hospital or treatment centre (if relevant and if accompanied by caregiver) • Time arrived back at hospital or treatment centre (if relevant) • Time left hospital or treatment centre to travel back to home/work • Time arrived back at home/work • Did caregiver take any time off work to attend this ERT episode? If yes, number of paid / unpaid hours absent from work. • Number of hours worked during ERT infusion (if relevant). • Costs (i.e. out-of-pocket expenses) incurred by the caregiver that were directly related to accompanying the patient for this ERT administration
---	--

	episode (to include costs of travel / parking / subsistence / any other costs).

Secondary objective 3: To describe patient-reported HRQoL (measured by the SF-12), wellbeing (measured by the WHO-5), levels of fatigue (measured by the bespoke Fatigue Likert scale) and work productivity (measured by the WPAI) in patients with FD treated with ERT (with agalsidase alfa or agalsidase beta).
	

Summary measures of patients':
 
 • HRQoL (SF-12 scores / responses). • General wellbeing (WHO-5 scores / responses). • Level of fatigue (bespoke Fatigue Likert scale). • Levels of work impairment (WPAI scores / responses). 
Questionnaire scores and/or item responses will be reported using summary statistics, as appropriate to the questionnaire and in accordance with the licensed scoring manual / instructions for use.
	
 • Patient SF-12, WHO-5, Fatigue Likert scale and WPAI responses and dates of completion. For the bespoke Fatigue Likert scale, times (hours and minutes) of completion will also be recorded.

Secondary objective 4: To describe work productivity (measured by the WPAI:CG) and the strain of care provision (measured by the CSI) in caregivers of patients with FD treated with ERT.
	

Summary measures of caregivers':
 
 • Levels of work impairment (WPAI:CG scores / responses). • Levels of strain of providing care for a patient with FD (CSI scores / responses). 	
 • Caregiver WPAI:CG and CSI responses and date of completion.

Questionnaire scores and/or item responses will be reported using summary statistics, as appropriate to the questionnaire and in accordance with the licensed scoring manual / instructions for use.
	

Patients' demographic and clinical characteristics (all patients)
	

Summary measures of (at date of consent, unless specified):
 
 • Sex. • Age at onset of first symptoms, at FD diagnosis and at date of consent. • Duration of ERT treatment. • ERT treatment. • FD phenotype (organs involved). • FD mutation ((if known)). • Severity of FD (to be determined using the specified baseline information]). • Any other relatives (with whom the patient lives) with FD. • Number and type (agalsidase alfa / agalsidase beta) of ERT infusions received in the year prior to date of enrolment. 	
 • Sex (male / female). • Date of consent. • Age at consent. • Age at onset of first symptoms. • Date of FD diagnosis. • ERT start date. • ERT treatment under observation (agalsidase alfa / agalsidase beta). • Number of ERT infusions received in the year prior to date of enrolment, by type of treatment (agalsidase alfa, agalsidase beta). • FD phenotype (organ involvement/complications), to include any current or prior history of: hypohidrosis, neuropathic pain (and/or acroparesthesia and/or acute pain crises), cornea verticillata, angiokeratomas, hearing impairment (including deafness and/or tinnitus), cardiac events (including rhythm and/or conduction disturbances, hypertrophic cardiomyopathy or left ventricular mass index [LVMi] above normal range, myocardial infarction

	
[MI], unstable angina, congestive heart failure, major cardiac medical procedures), renal events (including reduced estimated glomerular filtration rate [eGFR], abnormal albumin creatinine ratio [ACR], proteinuria or albuminuria, dialysis, kidney transplant), central nervous system (CNS) involvement (including brain magnetic resonance imaging [MRI] changes [white matter lesions], transient ischaemic attack [TIA] or stroke), FD-related gastrointestinal [GI] symptoms, plasma lyso-Gb3 levels above normal, low white blood cells (WBC) alpha-galactosidase, other: specify)
 
• eGFR at enrolment (closest measurement prior and preferably within 12 months); date and measurement.• Urine protein levels at enrolment (closest measurement prior); date and measurement.• WBC alpha-galactosidase (closest prior to enrolment); date and measurement• LVMi at enrolment (closest measurement prior and preferably within 12 months); date and measurement.
--	---

	
• FD mutation (name of mutation, if known, including: e.g. A143T)• Severity of FD (mild / moderate / severe), to be determined using the following baseline information:
○ Type of FD (classical / non classical). If type is unavailable, it will be inferred from the information collected below*.
▪ Number of organs involved (per medical history, as detailed above).▪ eGFR at enrolment.▪ Urine protein levels at enrolment.▪ LVMi at enrolment.▪ WBC alpha-galactosidase at enrolment.• Do any other relatives with whom the patient lives have FD (Yes / No / Not known).
	
*FD will be defined as classical if (1) multi-organ disease at baseline (≥ 2 organs) as determined by medical history or baseline values for eGFR, urine protein, LVMi, AND (2) white blood cells alpha-

	galactosidase below cut-off at baseline (≤3% wild-type).
--	---

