Enzyme replacement therapies (ERT) with agalsidase alfa (Replagal®, Shire) and with agalsidase beta (Fabrazyme®, Sanofi Genzyme) currently represent two treatment options for patients with FD and have been shown to reduce substrate levels in several cell types. In addition there are reports of reductions in the severity of neuropathic pain, stabilization of renal and cardiac function and delay in the occurrence of serious complications^{7–10}. However, both ERT preparations need to be administered as an intravenous (IV) infusion every two weeks and therefore lifelong ERT places a considerable burden on patients, their caregivers and healthcare services. ERT administered in the hospital or clinic setting requires frequent visits for IV infusions, which many patients find stressful and inconvenient; furthermore, hospital-based treatment often takes place in a specialist FD centre, which may be a considerable distance from the patient's home^{11,12}. In some countries ERT can be administered in the patient's home under certain circumstances (for example, if the patient has stable disease and experienced no adverse reactions during hospital-based infusion) and this is generally perceived to be more convenient than hospital-based therapy^{11–13}, can improve treatment compliance¹⁴ and may help to reduce the burden on healthcare services. However, even home-based ERT administration can cause disruption to a patient's daily activities and usually requires a healthcare professional (HCP) to supervise the infusion. To mitigate risk of adverse effects associated with ERT, patients are also frequently administered pre-medications with antihistamines and low-dose corticosteroids, which can be an added burden to patients.

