No queries will be raised on patient- or caregiver-reported data.

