
Start and end time of infusion (and pre-medication) preparation activities (note: the following activities [as appropriate] will be included in the total time, but the time for each separate activity will not be recorded]: pre-dispensing prescription review, label generation, collation of items prior to assembly, assembly of item/drug reconstitution, labelling of containers, accuracy check, prescription delivery).
	

ERT Infusion Procedure (and pre-medication) administration:
	
Time patient left – Time patient arrived

	
End time – Start time

Time patient arrived in clinic for ERT administration to begin
 
Time patient left clinic following completion of ERT administration
 
Start and end time of pre-medication administration.
 
Start and end time of ERT infusion.
 
Start and end time of HCP activity for administration of IV agalsidase alfa or agalsidase beta (including administration of pre-medications).
 
Start and end time of HCP activity for patient monitoring during agalsidase alfa or agalsidase beta infusion
 
Post-infusion administration assessment and documentation:
 
Start and end time of HCP activity for post-treatment patient assessment / monitoring.
 
Start and end time of HCP activity for completion of clinical documentation.
 
Other ERT-administration related activities
 
Start and end time of HCP activity for any other ERT administration related activities (specify).
	
End time – Start time
 
End time – Start time
 
End time - start time
 
End time – Start time

--	---

Secondary Objective 1

To quantify the total patient time, costs (i.e. out-of-pocket expenses) and work-related absence associated with attendances for the administration of a single dose of ERT (with agalsidase alfa or agalsidase beta) in patients with FD.

Summary measures of the total patient time associated with
	
--	--

attendance for the administration of a single dose of ERT (with agalsidase alfa or agalsidase beta) in patients with FD.
	
The difference between two time points will be calculated in minutes and will be summarized as per section 2.5 for quantitative variables for the following measures.

Time spent travelling to and from the hospital or treatment centre
	
Time left home – Time arrival at hospital

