
Summary measures of the total caregiver time associated with accompanying a patient with FD for the administration of a single dose of ERT (with agalsidase alfa or agalsidase beta).
 
Demographics for caregiver
 
 ○ Sex ○ Age category ○ Has FD or not ○ Employment status ○ Relationship to patient ○ Type of care ○ Frequency of care 
 ○ Time left home/work to travel to hospital or treatment centre ○ Time arrived at hospital or treatment centre ○ Time of start of ERT infusion ○ Time left hospital or treatment centre to travel back to home/work ○ Time arrived back at home/work. 
If the patient started their ERT infusion at home following set-up at a primary healthcare centre, the following will also be collected (if the caregiver was involved in the activity)
 
 ○ Start and end time of ERT infusion 	
The frequency distribution and percentage for each category of the demographic variable will be given.
 
The difference between these two time points in minutes will be summarized as in section 2.5 for quantitative variables.
 
The difference between start and end time (in minutes) of these will be calculated and summary statistics will

--	---

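### Travel times are listed with no date of their own, and the SAP has no rule for journeys that cross midnight, so those journeys cannot be derived reliably.

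*Protocol*

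**What the plan says.** Protocol 9.6, Table 4 (secondary objectives 1 and 2), lists a single date item, "Date of episode", on the bespoke patient questionnaire and again on the caregiver questionnaire. The journey items are times with no date attached: "Time left home/work to travel to hospital or treatment centre", "Time arrived at hospital or treatment centre", departure from the centre, and "Time arrived back at home/work". For patients who infuse at home after set-up at a primary care centre, a possible second trip to the centre is listed in the same way.

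One patient item touches on the next day: whether the patient went back to work on the infusion day or the day after. It does not date the departure from home or the arrival home. No such item is listed for caregivers.

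For patient times, SAP 2.6 states: "The difference between two time points will be calculated in minutes and will be summarized as per section 2.5 for quantitative variables". For caregivers it states: "The difference between these two time points in minutes will be summarized as in section 2.5 for quantitative variables". Neither part has a rule for times on different days or for negative differences. The order of subtraction also varies. For patients, the outbound leg and the wait from arrival to infusion are written start minus end. The infusion and the main journey home are written end minus start. The caregiver rows give no order.

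Protocol 9.10 adds: "No queries will be raised on patient- or caregiver-reported data". Protocol 10.1 and SAP 3.2 limit independent review to the primary endpoint, and Protocol 9.9.4 plans no sensitivity analyses.

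**The concern.** Subtracting clock times is valid only if both fall on the same date. The background section of the protocol says treatment often takes place "in a specialist FD centre, which may be a considerable distance from the patient's home", so travel the day before, or a return after midnight, is foreseeable for some patients and caregivers. With the listed fields the analyst cannot tell a two-hour trip from one that took a day longer.

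Total patient time and total caregiver time are main secondary endpoints. The people affected would be those with the longest journeys. Respondents will not be asked to clarify, and no second analyst checks these endpoints. A negative value is not a dependable warning either, because under the SAP's outbound formula every ordinary same-day trip is already negative.

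**Working it through.** The documents give no figure for this point, so there is none to reproduce. The check applies clock arithmetic to assumed journeys and then works out the effect on a mean.

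**Inputs from the documents.** One date per questionnaire and undated journey times (Protocol Table 4). Subtraction orders as written in SAP 2.6. About 30 patient and 5 caregiver questionnaire sets per country, 120 and 20 in total (Protocol 9.8, SAP 2.4).

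**Assumptions.** The journeys below are illustrative. A group of 15 is an even split of a country's 30 patients between the two products.

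**Step 1: single legs, in hours.** The last column adds 24 h to any negative end-minus-start value.

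| Assumed leg | True | End − start | Start − end (SAP outbound) | +24 h if negative |
|---|---|---|---|---|
| Out, 07:00 to 10:00, same day | 3 | 3 | −3 | 3 |
| Out, 14:00 day before to 08:00 | 18 | −6 | +6 | 18 |
| Out, 22:00 day before to 06:00 | 8 | −16 | +16 | 8 |
| Out, 06:00 day before to 08:00 | 26 | 2 | −2 | 2 |
| Return, 21:00 to 01:00 next day | 4 | −20 | n/a | 4 |
| Return, 16:00 to 18:00 next day | 26 | 2 | n/a | 2 |
| Return, 16:00 to 12:00 two days later | 44 | −4 | n/a | 20 |

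Reading the table:

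- End minus start is short by 24 h (1440 min) per midnight crossed: −6 − 18 = −24, and −4 − 44 = −48.
- A leg under 24 h that crosses midnight comes out negative, and adding 24 h restores it exactly.
- The two 26 h legs read as 2 h. That looks ordinary, and nothing in the listed fields reveals the loss.
- The 44 h leg is visibly negative, but adding 24 h gives 20 h, still 24 h short.
- The literal outbound formula turns 18 h into 6 h (12 h short) and 8 h into 16 h (8 h too long). Taking absolute values to tidy the signs gives the same two results.

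**Step 2: effect on a mean under end minus start, left uncorrected.** Shift = −1440 × k / n, for k respondents who each cross one midnight.

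- n = 30 patients in a country: k = 1 gives −48 min; k = 3 gives −144 min.
- n = 15 patients: k = 1 gives −96 min.
- n = 5 caregivers in a country: k = 1 gives −288 min.
- All countries: k = 1 gives −12 min among 120 patients and −72 min among 20 caregivers.

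A respondent who crosses midnight both ways counts twice.

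**Step 3: range over the unknown frequency.** With 0, 1 or 3 of 30 patients affected (0%, 3%, 10%, all assumed), the country mean shifts by 0, −48 or −144 min.

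**Step 4: with a date for each time.** End minus start on date-time returns the true duration for every leg in the table, so the error is zero.

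**The case against.** A reader might infer that every overnight journey will come out 24 hours too short and that the study must therefore understate travel burden. The documents do not support that reading.

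- The SAP's outbound formula is start minus end. Its error on a leg that crosses midnight is not a uniform 24-hour loss and can be an overestimate.
- Under end minus start, legs shorter than 24 hours are visibly wrong and recoverable. Nothing says negative values would be averaged as they stand.
- No passage mentions overnight travel or its frequency. The remark about distance is general background, and in some countries infusion or set-up takes place at community centres. Medians and IQRs are planned too (SAP 2.5), and one traveller in 30 barely moves them.
- Protocol 9.6 calls the listed response categories indicative and leaves the final list to the CRF. The questionnaires are not in the text available, so the form may already carry dates.
- The plan does not say whether a night spent near the centre counts as travelling, so 26 hours is not beyond dispute as the true value.

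All five points stand, and they limit the claim. They do not remove it. The SAP is the place for the derivation rule and has none, whatever the form holds. Its two subtraction orders conflict. A silent loss on a leg of 24 hours or more cannot be recovered from the listed fields, and with no queries or second check on these endpoints, even visible errors depend on the analyst's judgement.

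**Conclusion.** The gap is real but limited. As listed, the fields and the SAP formulas cannot give a reliable duration for a leg that crosses midnight. Under end minus start, the error is 1440 min per midnight crossed. It is visible and recoverable for legs under 24 hours and silent for many longer ones. Under the outbound formula as written, the error can go either way.

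The shifts of 48, 96 and 288 min per affected journey assume that the form follows Table 4, that end minus start is used, that one midnight is crossed, that the elapsed overnight time counts, and that the value is left uncorrected. Neither the size nor the direction of any overall bias can be stated. The primary endpoint does not use these questionnaire times. This is a cheap improvement that protects two main secondary endpoints, and it is best made before questionnaires are issued.

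**What to change.** 1. **Form and Table 4.** Beside each departure and arrival time on the bespoke patient and caregiver questionnaires, add a day indicator: day before, day of infusion, day after, or other date. Use the same item when answers are taken by telephone. If the form already has this, bring Table 4 into line.
2. **SAP 2.6.** Define every travel and stay component, for patients and caregivers, as end minus start on date-time, and correct the rows written the other way round. State whether an overnight stay counts as travel or is reported separately. Report the number of overnight journeys.
3. **Forms already returned without the indicator.** Add 24 hours to a negative end-minus-start difference, flag it, and show results with and without flagged values. Do not set such values to missing, because that discards recoverable data from the people who travel furthest. State as a limitation that silent losses on legs of 24 hours or more remain, and that a leg over two midnights may still be 24 hours short.

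The cost is a slightly longer form, re-issue of the translated versions, and a short addition to the SAP.
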